### 9.2.2 Device Deficiency

Device deficiency information will be collected throughout the study and reported to Medtronic. Note that device deficiencies that result in an adverse device effect (ADE) to the subject should be captured as an Adverse Event only.

Device deficiencies that did not lead to an AE but could have led to a Serious Adverse Device Effect (SADE) (i.e., if suitable action had not been taken, if intervention had not been made, or if the circumstances had been less fortunate) require immediate reporting (see Table 9).

Initial reporting may be done on the CRF completing as much information as is available. The original completed Device Deficiency CRF must be sent to Medtronic as soon as possible.

### 9.2.3 Processing Updates and Resolution

For any changes in status of a previously reported adverse event (i.e. change in actions taken, change in outcome, change in relatedness), an update to the original AE must be completed. All reported adverse events must be followed until the adverse event has been resolved, is unresolved with no further actions planned, the subject exits the study or until study closure, whichever occurs first.

In the event that a subject is exited from the study prior to study closure, all efforts should be made to continue following the subject until all reported adverse events are resolved or they are unresolved with no further actions planned.

At the time of study exit, all adverse events with an outcome of “Unresolved, further actions or treatment planned” must be reviewed and an update to the original AE must be reported. At a minimum, if there are no changes to the description, relatedness, test and procedures or actions taken, the outcome must be updated to reflect “Unresolved at study exit.”

## 9.3 Market-released reporting requirements

Product complaint reporting is applicable to devices that are market-released. This includes when an AE is related to a market-released device during the study. The reporting of product complaints is not part of the clinical study and should be done in addition to the Adverse Event reporting requirements. Refer to local regulations for reporting requirements.

**Product Complaint:** Any written, electronic or oral communication that alleges deficiencies related to the identity, quality, durability, reliability, safety, effectiveness or performance of a medical device that has been placed on the market.

It is the responsibility of the investigator to report all product complaint(s) associated with a medical device distributed by Medtronic, regardless whether they are related to intended use, misuse or abuse of the product. Reporting must be done immediately and via the regular channels for market-released products.

Medtronic will notify the regulatory authorities as applicable for the following incidents immediately upon learning of them:

- Any malfunction or deterioration in the characteristics and/or performance of a device, as well as any inadequacy in the labeling or instructions for use which led or might have led to the death or serious deterioration in the state of health of a patient, user, or other person.
- Any technical or medical reason resulting in withdrawal of a device from the market by the manufacturer.
- A serious deterioration in the state of health includes:
  - Life-threatening illness or injury
  - Permanent impairment of a body function or permanent damage to a body structure
  - A condition necessitating medical or surgical intervention to prevent permanent impairment to a body structure or a body function

## 9.4 Adverse event and reporting requirements

Regulatory reporting of AEs will be completed according to regulatory requirements. Refer to Table 9: Adverse Event Reporting for a list of required investigator reporting requirements and timeframes, and of required Medtronic reporting requirements and timeframes.

It is the responsibility of the investigator to abide by any additional AE reporting requirements stipulated by the IRB/MEC.

For AEs that require immediate reporting, initial reporting may be done by contacting the study sponsor per the sponsor contact information provided in this document.

Table 9: Adverse Event and Device Deficiency Reporting Requirements

Unanticipated Adverse Device Effects (UADEs)	
Investigator submit to:	
Medtronic	US: Submit as soon as possible, but no later than within 10 working days after the investigator first learns of the event. (21 CFR 812.150(a)(1)) Europe: Immediately after the Investigator first learns of the event or of new information in relation with an already reported event.
IRB/MEC	US: Submit as soon as possible, but no later than within 10 working days after the investigator first learns of the event. (21 CFR 812.150(a)(1)) Europe: Submit to MEC per local reporting requirement.
Regulatory Authorities	Europe: Submit to regulatory authority per local reporting requirement.
Sponsor submit to:	
Investigator	All geographies: Submit as soon as possible, but no later than within 10 working days after the sponsorfirst learns of the event. (21 CFR 812.150(b)(1))
Regulatory authorities	US: Submit as soon as possible, but no later than within 10 working days after the sponsorfirst learns of the event. (21 CFR 812.150(b)(1)) Europe: Submit to regulatory authorities per local reporting requirement.
IRB/MEC	US: Submit as soon as possible, but no later than within 10 working days after the sponsorfirst learns of the event. (21 CFR 812.150(b)(1)) Europe: Submit to IRB/MEC per local reporting requirement
All other Adverse Events	
Investigator submit to:	
Medtronic	All geographies: Submit or report as required for local reporting requirements and protocol.
IRB/MEC	All geographies: Submit to IRB/MEC per local reporting requirements.
Regulatory authorities	All geographies: Submit to regulatory authority per local reporting requirement.
Sponsor submit to:	
Regulatory Authorities	All geographies: Submit to regulatory authority per local reporting requirement.
Device Deficiencies with SADE Potential	
Investigator submit to:	
Medtronic	All geographies: Submit or report as required for local reporting requirements and protocol.
IRB/MEC	All geographies: Submit to IRB/MEC per local reporting requirements.
Regulatory authorities	All geographies: Submit to regulatory authority per local reporting requirement.

Sponsor submit to:	
Regulatory Authorities	All geographies: Submit to regulatory authority per local reporting requirement.
All other Device Deficiencies	
Investigator submit to:	
Medtronic	All geographies: Submit in a timely manner after the investigator first learns of the event.
IRB/MEC	All geographies: Submit to IRB/MEC per local reporting requirements.
Regulatory authorities	All geographies: Submit to regulatory authority per local reporting requirement.

## 9.5 Subject death

### 9.5.1 Death Data Collection

All subject deaths must be reported by the investigator to Medtronic on an adverse event CRF (SAE leading to death) as soon as possible after the investigator first learns of the death. There should be one SAE with the outcome of death.

A copy of the death certificate, if available and allowed by state/local law, should be sent to the Medtronic clinical study team. When a death occurs in a hospital, a copy of the death summary report and all relevant hospital records should be sent to the Medtronic clinical study team, if available. If an autopsy is conducted, the autopsy report should also be sent to the Medtronic clinical study team if available and allowed by state/local law. When the death occurs at a remote center, it is the investigative center's responsibility to attempt retrieval of information about the death. In summary, the following data will be collected:

- Date of death
- Detailed description of death
- Cause of death
- Relatedness to system and/or procedure
- Death summary/hospital records (if available and allowed by state/local law)
- Autopsy report (if available and allowed by state/local law)
- Death certificate (if available and/or allowed by state/local law)

### 9.5.2 Death Classification and Reporting

Sufficient information will be required in order to properly classify the subject's death. The Investigator shall classify each subject death per the following definitions:

Cardiac Death: A death directly related to the electrical or mechanical dysfunction of the heart.

Sudden Cardiac Death (SCD): Natural death due to cardiac causes, indicated by abrupt loss of consciousness within one hour of the onset of acute symptoms; preexisting heart disease may have been known to be present, but the time and mode of death are unexpected. If time of onset cannot be determined, SCD will alternatively be defined as any unexpected cardiac death occurring out of the hospital or in the

emergency room as dead on arrival.

Non-sudden Cardiac Death: All cardiac deaths that are not classified as sudden deaths, including all cardiac deaths of hospitalized subjects on inotropic support.

Non-cardiac Death: A death not classified as a cardiac death.

Unknown Cardiac Classification: Unknown death classification is intended for use only when there is insufficient or inadequate information to classify the death.

The CEC will review deaths and provide a final adjudication of the cardiac classification.

## 9.6 CEC review

At regular intervals, an independent CEC will conduct a medical review of, at a minimum, all deaths and endpoint related events.

The CEC will consist of a minimum of three (3) non-Medtronic employed physicians that are not participating investigators for the study, including a CEC chairperson. At least two CEC members must adjudicate, at a minimum, all deaths and serious AEs related to any component of the systems under investigation. All other events may be adjudicated by at least one member of the CEC.

The CEC members may be blinded to the subjects' randomization assignment and/or other data or procedures that may influence their decision.

Medtronic personnel may facilitate and participate in a CEC meeting but will be non-voting members.

For adverse events, and deaths, reviewed by the CEC, Medtronic will provide the CEC with the Investigator's description and classification. The CEC is responsible for reviewing the Investigator's assessment and supportive documentation (when available), reviewing applicable definitions, and determining final classifications for all adjudication parameters.

If the CEC disagrees with the investigator's classification of the event, the rationale will be provided to the investigator. If the investigator agrees with the CEC's adjudication, the CRF documenting the AE or AE update will be updated accordingly.

If the investigator does not agree with the CEC's adjudication classification, both determinations will be provided within the final report; however, the CEC's adjudication will be used for data analysis. The disagreement will also be included in reporting to IRB/MEC and regulatory authorities, if required.

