#### **6.9 Randomization**

Randomization schedules will be prepared for each site using a random permuted block design stratified by center and AF diagnosis. The schedules will allocate subjects in a 1:1 ratio to the treatment or control arm.

Each center will receive a set of sequentially numbered envelopes labeled specifically for that center that is labeled with one randomization code per envelope. After a CT scan has been performed and confirmed that the renal anatomy meets eligibility requirements, the subject will be randomized.

The next sequential envelope labeled with a randomization code will be used. The envelope number will be recorded for each randomized subject and communicated to Medtronic. The sequence of subject randomization will be checked to ensure it matches the sequence of envelope numbers.

Randomization assignments are the following:

- Treatment:
  - Perform the pulmonary vein isolation procedure, renal angiogram, renal artery denervation procedure and the Reveal LINQ insertion.
- Control:

- Perform the pulmonary vein isolation procedure and the Reveal LINQ insertion. Do NOT perform renal denervation.

Enrolled subjects who were not randomized should be exited. See Section 9.2.2 if the subject has an ongoing adverse event.

Subjects and center personnel will be blinded to the randomization assignment until after the pulmonary vein isolation procedure.

Crossing over to the Treatment group once assigned to the Control group is not allowed at any point during the study.

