## 6.23 Recurrence of atrial fibrillation

Documentation of AF recurrence must be provided to the sponsor and additional source documents may be requested. Documentation of AF must include the following:

- Reveal LINQ rhythm recording (EGM)

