## 9.2 Adverse event and device deficiency assessment

### 9.2.1 Adverse Events

To ensure that all AEs which are potentially relevant are collected, all system related, procedure related, cardiovascular related and serious AEs will be collected throughout the study duration, starting at the time of signing the consent form. Reporting of these events to Medtronic will occur on an AE form, including a description of the AE, date of AE onset, treatment, resolution, and assessment of both the seriousness and the relatedness to the device.

Exceptions include:

- Documented pre-existing conditions are not considered AEs unless the nature or severity of the condition has worsened
- Recurrence of AF event unless an invasive action was taken
- Unavoidable AEs unless the AE worsens or is present outside the stated timeframe listed in Table 8

For AEs that require immediate reporting (see Table 9: Adverse Event Reporting), initial reporting may be done by phone, fax, email or on the CRF completing as much information as possible. The completed AE CRF must be submitted to Medtronic as soon as possible. Each AE must be recorded on a separate AE Form. Subject deaths are also required to be reported. Refer to Section 9.5 for Subject Death collection and reporting requirements.

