The Clinical Event Committee (CEC) members may be blinded to the subjects' randomization assignment and/or other data or procedures that may influence their decision.

More details can be found in the Symplicity AF Randomization and Blinding Plan document.

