5.5. Endpoint Adjudication

An independent CEC will conduct a medical review of, at a minimum, all deaths and adverse events (AE). The CEC's adjudication will be used for data analysis.

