7.11. Safety Evaluation

A summary table of AEs by classification the following classifications will be reported:

- Serious Adverse Events (SAE)
- Unanticipated Adverse Device Effects (UADE)
- Complication or observation
- Procedure relatedness
- System relatedness

A second table will be reported summarizing AEs by MedDRA preferred term.

The tables will show the counts of the number of a specified AE classification (e.g., SAE, MedDRA term, etc.) and the number of subjects who experienced the specified AE classification, and calculate the percentage of subjects who experience the specified AE classification.

A listing of all AEs will be reported with one row per AE.

All AEs for the enrolled analysis set will be included. The CEC classification of AEs will be used, except for SAEs and UADEs, where the Medtronic classification will be used since those are not adjudicated by the CEC.

Example summary table (the final validated version may differ)

Number of Events (Number, % Subjects)	Subjects Not Randomized (N = N _S)	Subjects Randomized (N = N _S)	Subjects Enrolled (N = N _S)
Total Adverse Events	177 (116, 35.3%)	177 (116, 36.4%)	177 (116, 36.4%)
Serious Adverse Event			
Yes	97 (66, 20.1%)	97 (66, 20.7%)	97 (66, 20.7%)
No	80 (64, 19.5%)	80 (64, 20.1%)	80 (64, 20.1%)
Unanticipated Adverse Device Effect			
Yes	0 (0, 0.0%)	0 (0, 0.0%)	0 (0, 0.0%)
No	177 (116, 35.3%)	177 (116, 36.4%)	177 (116, 36.4%)
Complication or Observation			
Complication	0 (0, 0.0%)	0 (0, 0.0%)	0 (0, 0.0%)
Observation	177 (116, 35.3%)	177 (116, 36.4%)	177 (116, 36.4%)
Procedure Relatedness			
Related	49 (43, 13.1%)	49 (43, 13.5%)	49 (43, 13.5%)
Cryoablation	49 (43, 13.1%)	49 (43, 13.5%)	49 (43, 13.5%)
Repeat cryoablation	0 (0, 0.0%)	0 (0, 0.0%)	0 (0, 0.0%)
Renal angiogram	N _E (N _S , % _S)	N _E (N _S , % _S)	N _E (N _S , % _S)
Renal CT	N _E (N _S , % _S)	N _E (N _S , % _S)	N _E (N _S , % _S)
Renal denervation	N _E (N _S , % _S)	N _E (N _S , % _S)	N _E (N _S , % _S)
Reveal LINQ	N _E (N _S , % _S)	N _E (N _S , % _S)	N _E (N _S , % _S)
Other	N _E (N _S , % _S)	N _E (N _S , % _S)	N _E (N _S , % _S)
Not Related	126 (83, 25.2%)	126 (83, 26.0%)	126 (83, 26.0%)
Unknown	2 (2, 0.6%)	2 (2, 0.6%)	2 (2, 0.6%)

Number of Events (Number, % Subjects)	Subjects Not Randomized (N = Ns)	Subjects Randomized (N = Ns)	Subjects Enrolled (N = Ns)
Cryoablation	49 (43, 13.1%)	49 (43, 13.5%)	49 (43, 13.5%)
Repeat cryoablation	0 (0, 0.0%)	0 (0, 0.0%)	0 (0, 0.0%)

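### The plan permits but does not require the events committee that classifies the primary safety endpoint to be blinded, and it does not settle who decides seriousness for that endpoint

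*Protocol*

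**What the plan says.** **Blinding.** CIP 6.9 states: "Subjects and center personnel will be blinded to the randomization assignment until after the pulmonary vein isolation procedure". SAP 5.3 repeats this. Control subjects have no renal angiogram and no denervation, and no sham is described, so all follow-up takes place with the arm known at the site.

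**The CEC.** CIP 9.6: "The CEC members may be blinded" to the assignment or to other information that could sway their decision. SAP 5.3: "The Clinical Event Committee (CEC) members may be blinded to the subjects' randomization assignment". SAP 5.3 then refers the reader to a separate Randomization and Blinding Plan. CIP 9.6 also says that the sponsor gives the CEC the investigator's own description and classification of each event.

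**Primary safety.** CIP 12.3 and SAP 7.10.1.3 require a composite event to be serious, and both use the CEC adjudication to classify subjects.

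**Seriousness.** CIP 9.6 makes the CEC responsible for the final classification on all adjudication parameters. Table 10 in CIP 9.7 assigns SAE status to the investigator and the sponsor. SAP 7.11 uses CEC classifications for adverse events except for SAEs and UADEs, "where the Medtronic classification will be used since those are not adjudicated by the CEC".

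**AF recurrence.** Failure under CIP 12.4 is a documented AF episode on Reveal LINQ, or an AF intervention, after day 90. CIP 6.23 says: "Documentation of AF recurrence must be provided to the sponsor and additional source documents may be requested". CIP 9.2.1 lists among the exceptions to adverse event reporting: "Recurrence of AF event unless an invasive action was taken". SAP 5.5 sets the minimum CEC review at deaths and adverse events, while CIP 9.6 sets it at deaths and endpoint related events.

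**The concern.** When sites and subjects know the arm, an independent committee that does not know it is the usual remaining protection for endpoints that need judgement. Here the committee's independence is required and its blinding is optional.

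Several safety components call for judgement: whether a groin haematoma is clinically significant, whether an arrhythmia is new or worse, and what counts as cardiac damage. The threshold of seriousness adds another. A reader who knows that a subject had the extra procedure may set these thresholds differently by arm. The product would be a biased difference in event rates, which CIP 12.3.3 says will guide the design of a pivotal trial.

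The same question arises, less directly, for AF recurrence. The plan does not say whether the device flag is itself the endpoint or whether a person must confirm it, and no blinded reader is named if one is needed.

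**Working it through.** **1. Blinding of the safety adjudication.** Three statements combine:
- Site blinding ends after the PVI (CIP 6.9).
- The CEC's adjudication is the endpoint classification (CIP 12.3, SAP 7.10.1.3).
- CEC blinding is permitted, not required (CIP 9.6, SAP 5.3).

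Together they allow every person who classifies a composite event to know the arm without any deviation from the plan. The list of bias measures in CIP 5.3 names an independent CEC and an independent DMC, but says nothing about either being blinded to assignment.

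**2. Source of seriousness.**

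| Place | Who decides that an event is serious |
|---|---|
| CIP 9.6 | CEC, if seriousness is an adjudication parameter |
| CIP 9.7, Table 10 | Investigator and sponsor |
| CIP 12.3, SAP 7.10.1.3 | Event must be serious; CEC classifies subjects; source of the serious flag not stated |
| SAP 7.11 | Sponsor, for the adverse event tables |

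Table 10 is not decisive on its own. It has no CEC row at all, even for cardiac classification of death, where CIP 9.5.2 gives the CEC the final word. The five places can be read either way and need to be reconciled.

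**3. The plan's own effectiveness figure.** SAP Table 1 gives 17.6% + 10.1% + 50.9% = 78.6% power. With HR = ln(0.75)/ln(0.50) = 0.415, looks at 14, 19 and 41 events and Z bounds 2.576, 2.611 and 2.049, a Brownian-motion simulation returns 17.6%, 10.1% and 50.9%, total 78.6%, with a two-sided alpha of 0.0497. The design reproduces.

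**4. Sensitivity of the log-rank test to one-sided dismissal.** Inputs from CIP 12.4.6 and the SAP: 35 per arm, 16 months' accrual, 22-month study, 5% dropout per 6 months. Assumptions:
- no true effect;
- 50% failure at 6 months in both arms, so the hazard is ln(2)/6 per month;
- one final look at two-sided p ≤ 0.04, that is Z < -2.054;
- a share of Treatment failures dismissed and no Control failures.

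Each scenario had 20,000 trials. At a rate of 3% the simulation error is √(0.03 × 0.97/20,000) = 0.0012, or 0.12 percentage points.

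| Treatment failures dismissed | False win if every later episode is also dismissed |
|---|---|
| 0% | about 2% |
| 5% | about 4.5% |
| 10% | about 8.5% |
| 15% | about 14.5% |

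The 5% row averages 1.3 subjects, each kept event-free to the end of follow-up. If dismissal only postpones failure to a later episode, the rates across 5% to 15% dismissal are about 2.5% (mean delay 1 month) and about 2.6% to 3.6% (mean delay 3 months). Both delays are assumptions.

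**5. Cross-check with the three-look design.** If a share m of Treatment failures is lost for good, the apparent HR is ln(1 - 0.5(1 - m))/ln(0.5). For m = 5%, 10% and 15% this is 0.930, 0.862 and 0.798. With the planned looks and 41 events, false wins are 4.1%, 6.6% and 10.2%, from a base of 2.5%. The direction is the same and the rise is smaller.

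**The case against.** **AF detection is automatic.** The LINQ algorithm detects AF (CIP 3.2), programming is fixed with the ECG of all episodes recorded (CIP 6.14.1), data are transferred monthly (CIP 6.18.2), and only a LINQ recording counts as documentation (CIP 6.23). No section lets a site discard a detected episode. A reader might infer that an unblinded site can erase a failure by rejecting one strip. The documents do not support that, because a subject with recurring AF goes on producing recordings. This objection largely stands, which is why effectiveness is secondary here. What remains is that CIP 10 lists over- and under-sensing as a LINQ risk, and the plan does not say who, if anyone, confirms a flagged episode.

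**Scope and unseen documents.** CIP 9.6 puts endpoint related events within CEC review, which can be read to include AF recurrence. The Randomization and Blinding Plan and the CEC charter were not available, nor were the core-lab and committee pages. A reader might infer that no blinded assessor exists for either primary endpoint. That can be said only of the CIP and SAP text supplied.

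**Seriousness.** SAP 7.11 governs adverse event tables. A reader might infer that the sponsor decides seriousness for the composite; the endpoint sections do not say so. Several components also carry seriousness in their definition: death, renal disease requiring dialysis, renal artery events requiring intervention, hospitalization for hypertensive crisis. This stands as a limit on the point, but the conflict between sections remains.

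**Stakes.** Primary safety has no hypothesis and no performance requirement. That removes any pass or fail consequence, but the estimated difference can still be biased.

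**Conclusion.** The point holds for primary safety. On the supplied text, unblinded adjudication of the composite complies with the plan, and the source of seriousness is unresolved across five places. The documents offer no figure from which to size the resulting bias. The case for change is that the protection is cheap and the committee already exists.

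For primary effectiveness the point is minor. False-win rates of about 4.5%, 8.5% and 14.5% require that every later episode in a dismissed subject is also dismissed. With a mean delay of 1 to 3 months the range is about 2.5% to 3.5%, against about 2% with unbiased reading. The documents give no basis for choosing a dismissal rate, so none of these is a forecast, and the 14.5% figure should not be cited alone. The decision to intervene for AF, the other component of failure, is made with the arm known, and blinded reading of recordings cannot protect it.

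If the Randomization and Blinding Plan or the CEC charter already requires blinding, what remains is to state that in the CIP and SAP.

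**What to change.** 1. **CIP 9.6 and SAP 5.3.** Replace the permissive wording with a requirement that CEC members *will be blinded to randomization assignment*, with arm-identifying text redacted from event packets except where the event itself reveals renal denervation. Cost: wording, a check against the CEC charter, and sponsor redaction time. Masking will be incomplete for renal events.
2. **CIP 9.6, 9.7 (Table 10) and 12.3; SAP 7.10.1.3 and 7.11.** Reconcile these so that the blinded CEC determines seriousness for candidate safety composite events. The sponsor's classification can stay for the general adverse event tables. Cost: wording and a small addition to CEC workload.
3. **Secondary: CIP 6.23 and 12.4; SAP 7.10.2.3.** State whether the device detection alone defines an AF failure. Where a person must confirm that a LINQ-detected episode is AF, the CEC should do so from the EGM without arm or site. About 41 primary events are planned, but the reading load may be larger, because false-positive strips before the first confirmed episode would also have to be read.

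None of these needs a new visit, procedure or committee.
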